#### 10.4.6 BASELINE DESCRIPTIVE STATISTICS

Demographic statistics (# and % male/female, %ethnicity, % race) will be collected and reported.

## 10.4.7 PLANNED INTERIM ANALYSES

### 10.4.7.1 SAFETY REVIEW

As this is a low-risk study, no specific safety review will be conducted. See the handling of Adverse Events for mechanisms for safety assurance.

### 10.4.7.2 EFFICACY REVIEW

N/A

## 10.4.8 ADDITIONAL SUB-GROUP ANALYSES

N/A

## 10.4.9 MULTIPLE COMPARISON/MULTIPLICITY

The planned analyses do not include multiple comparisons.

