## 3 OBJECTIVES AND PURPOSE

This study will evaluate the safety and effectiveness of Shade for the management of UV-induced skin complications and data collected from this study will be used to support the proposed indications for use.

The purpose of this investigation is to demonstrate the safety and effectiveness of the Shade UV sensor and mobile

phone application product to reduce actinic keratosis.

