## 4 STUDY DESIGN AND ENDPOINTS

### 4.1 DESCRIPTION OF THE STUDY DESIGN

This randomized partially blinded study will recruit 120 patients with a history of actinic keratosis (AK) lesions. A control versus study group analysis will be performed where 50% of the subjects will be randomly assigned (balanced by Fitzpatrick skin type, separate randomization lists will be made for type I&II and types III-VI, at time of first visit subjects will be assigned to study or control group by giving them the next assignment on the appropriate list) to use the SHADE sensor and its app (study group), while the other 50% (control group) will receive standard of care UV counseling(placebo). Subjects will have 3 visits. The first and last visit will be standard of care visits at 0 month (enrollment), and the conclusion of their involvement. The second visit will be scheduled 3 months after the enrollment visit. The final visit will be scheduled as soon as practical, but at least 3 months after visit 2 and after September 30. On arrival at each visit, study personnel will pre-screen patients to ensure that the sensor is not visible to physician prior to examination, for example by placing it in their pocket. At each follow up visit, the number of actinic keratosis on the face and hands will be counted and photographed. They will be treated as per standard of care protocol with cryotherapy or curettage. General use of field therapies will not be permitted during the trial. Any lesions suspicious of non-melanoma or melanoma skin cancer will be photographed and biopsied as part of the standard of care algorithm. Cyclobutane pyrimidine dimers (CPD) levels will be measured by ELISA from exposed (cheek) and unexposed (buccal mucosa) skin scrapings collected at the first and last visit. For each patient, the CPD level from exposed skin will be normalized to the sun protected CPD level measured from unexposed skin. We will compare the normalized CPD level of control versus study participants at each timepoint and their average CPD change over time.

We will then compare these levels with Shade UV measurements. Finally, patients will also answer questions in PROMIS (Patient-Reported Outcomes Measurement Information System) in the fields of anxiety, depression and ability to participate socially to gauge their attitudes toward the sensor

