#### 10.4.1 GENERAL APPROACH

All tests will be two-tailed with the significance level set at 0.05. Analysis will be performed using STATA statistical software (StataCorp. 2015) or R (R: A language and environment for statistical computing. R Foundation for Statistical Computing, Vienna, Austria).

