#### 10.4.3 ANALYSIS OF THE SECONDARY ENDPOINT(S)

##### **#2 (Secondary): Quantify the impact of Shade on the numbers of new AK's observed at the final visit**

This analysis will follow the same procedure as the primary analysis but will only include AK data from the final visit.

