##### **#3 (Secondary): Quantify the impact of Shade on the numbers of new cutaneous squamous cell carcinomas confirmed by histology during follow up over the study period.**

To test the early effect of Shade on skin cancer risk and the robustness of our findings, we will perform a longitudinal analysis to test a reduction by at least 25% of squamous cell carcinoma. The effect of Shade use will be estimated using a single mixed linear model (with random intercept and slope) for repeated (longitudinal) data including study group and time since enrollment as explanatory variables. A similar stepwise multivariate approach with backward selection as described in the primary aim will be performed to take into account confounding factors.

**#4 (Secondary): Quantify the impact of Shade on the number of new nonmelanoma skin cancers (basal cell carcinomas, cutaneous squamous cell carcinomas) confirmed by histology over the study period.**

To test the early effect of Shade on skin cancer risk and the robustness of our findings, we will compare the cumulative numbers of new nonmelanoma skin cancers between the control and study group and test a reduction by at least 25% of non-melanoma skin cancer s as secondary outcome, using a t-test. A similar stepwise multivariate approach with backward selection as described in the primary aim will be perform to take into account confounding factors.

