To assess the impact of Shade on quality of life, patients will be surveyed using short form paper versions of PROMIS (Patient-Reported Outcomes Measurement Information System) scores in the fields of depression, anxiety, and the ability to participate in social roles and activities. PROMIS survey will be performed at each visit. We will compare the change in PROMIS scores between group and study using a t-test at each time-point.

The outcome will be assessed for statistical significance (p-value of change in PROMIS score between groups) and clinical significance (changes of 3 points on a single score are generally considered meaningful to subjects).

**#9 (Secondary): Assess sensor usage in the study patient population and compare characteristics of observant vs non-observant and responsive vs non-responsive patients.**

To assess sensor usage, we will estimate the overall percentage (and 95% confidence interval) of days used in the study patient population, the average (and standard deviation) and median (and quartile) of the daily UV threshold set by the patients and the percentage of days below and above the UV threshold.

The Shade sensor and the mobile application enables users to decide, by looking at self-reported symptoms and daily cumulative UV exposure over 15 and 30 days, how much UV exposure in J/m^2 they would like to manage per day, which we call the daily UV threshold. Users can select a daily UV threshold that is lower than their previous maximum daily UV exposure. Of course, users are free to go beyond this threshold if they chose to and the app will let them know in real time by how much they have exceeded their threshold. The threshold can be adjusted at any time through the app. The Shade app does not make any recommendation regarding the daily threshold. Note that each subject will be individually counseled to minimize UV exposure.

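### Section 10.4.9 says there are no multiple comparisons, yet 10.4.3 plans about 16 unadjusted secondary tests at two-sided 0.05, with no statement of how their p-values may be used

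*Combined protocol and SAP*

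**What the plan says.** Section 10.4.9 consists of one sentence: "The planned analyses do not include multiple comparisons". Section 10.4.1 sets a single rule for everything: "All tests will be two-tailed with the significance level set at 0.05".

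Section 10.4.3 then sets out the secondary analyses:

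- #2, actinic keratoses (AKs) counted at visit 3 alone, described thus: "This analysis will follow the same procedure as the primary analysis but will only include AK data from the final visit".
- For SCC (squamous cell carcinoma, #3): "The effect of Shade use will be estimated using a single mixed linear model", with the aim to "test a reduction by at least 25% of squamous cell carcinoma".
- #4, nonmelanoma skin cancer (NMSC): a t-test between arms, also directed at a 25% reduction.
- #5 and #6: correlations of cumulative UV with AKs (at each time point) and with NMSC, with a stated definition of a significant correlation.
- #7, CPD: arms compared at each time point and on change, plus a correlation with UV over the preceding 24 hours.
- #8, PROMIS: three domains, compared "using a t-test at each time-point".
- #9: t-tests and chi-square tests on the characteristics of usage groups, number not given.
- #10: rates only, expressly not tested.

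Section 4.1 gives the number of occasions: "Subjects will have 3 visits". Sections 4.2.3 and 10.4.11 list no exploratory endpoints or analyses. Section 3 says that "data collected from this study will be used to support the proposed indications for use".

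**The concern.** The multiplicity statement conflicts with the analyses listed just before it. Several secondary endpoints are tested more than once, over visits or domains, and no main PROMIS domain or visit is named. Only #10 is exempted from testing. Because the plan declares nothing exploratory, #2 to #8 cannot be taken as descriptive by default.

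What is at stake is how secondary results may be worded. An isolated p-value below 0.05 for SCC, NMSC, CPD or a PROMIS domain could be called significant, and 10.4.9 could be cited as the reason that no allowance was made. This matters most for #3 and #4, which the plan presents as evidence on skin cancer risk, a heavier claim than one about AK counts.

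**Working it through.** The documents give no family-wise error rate and no count of tests, so there is no stated figure to reproduce.

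**Step 1: count the tests in 10.4.3** (three visits, so two follow-up time points; section 4.1 has CPD sampled at the first and last visits).

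| Endpoint | Tests | Basis |
|---|---|---|
| #2 | 1 | between arms |
| #3 | 1 | between arms, mixed model |
| #4 | 1 | between arms |
| #5 | 2 | correlation at two follow-up time points |
| #6 | 1 | correlation |
| #7 | 4 | one UV correlation; arms at first visit, at last visit, and on change |
| #8 | 6 | three domains × two changes from baseline |

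Total: 1 + 1 + 1 + 2 + 1 + 4 + 6 = 16. Of these, 12 are between-arm tests (1 + 1 + 1 + 3 + 6). One of the 12 is the baseline CPD comparison; without it the total is 15. The count leaves out #9, the stepwise models attached to #2 to #4, and any visit 2 CPD comparison (the schedule in 7.3.7 marks a scraping there, while 4.1 does not).

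**Step 2: independent tests, all nulls true.** The chance of at least one p < 0.05 in k tests is 1 − 0.95^k.

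- k = 16: 0.560, with 16 × 0.05 = 0.8 false positives expected
- k = 15: 0.537
- k = 14: 0.512
- k = 13: 0.487
- k = 12 (between-arm only): 0.460

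One half is passed only from 14 independent tests upward.

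**Step 3: allow for dependence.** SCC is part of NMSC, CPD change is built from the two CPD levels, PROMIS is repeated in the same subjects, and UV dose is cumulative. The documents give no correlations, so the values below are assumptions. They were applied to jointly normal test statistics with all nulls true (400,000 draws), with no correlation between families.

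| Assumed correlation | PROMIS domains; PROMIS visits; SCC with NMSC | #5 time points | #6 with #5 | CPD visits | All 16 | 12 between-arm |
|---|---|---|---|---|---|---|
| Weak | 0.3 each | 0.5 | 0.1 | 0.2 | 0.53 | 0.43 |
| Moderate | 0.5 each | 0.7 | 0.2 | 0.4 | 0.51 | 0.41 |
| Strong | 0.7 each | 0.8 | 0.3 | 0.6 | 0.47 | 0.37 |

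With one common correlation across all 16 tests instead, the rate is 0.55 at 0.1, 0.52 at 0.2, 0.48 at 0.3 and 0.37 at 0.5.

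**Step 4: allow for direction.** #5 and #6 also require a value above 0.2, presumably the correlation coefficient. With 50 to 60 sensor users, a Pearson p < 0.05 already needs a coefficient of about 0.28 to 0.25 in size, so the condition serves only to fix the direction, at 0.025 per test. Dropping the baseline CPD test as well gives 1 − 0.95^12 × 0.975^3 = 0.499 under independence. Counting only false claims of benefit, at 0.025 for each of 16 tests, gives 1 − 0.975^16 = 0.333.

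**The case against.** The strongest reply is that the endpoints are labelled primary and secondary, there are two arms, and no efficacy interim or subgroup analysis is planned. On that view 10.4.9 may have meant only that the primary comparison is single, and unadjusted secondaries are a common reporting choice. That reading is possible, but the text does not say it, and one added sentence would be enough to make it true.

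Three further objections stand in part.

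- **Decision criteria differ.** Among the secondaries, only #7 has the full wording of a statistically significant reduction of at least 25%. #3 and #4 test a reduction of that size, #5 and #6 carry the 0.2 condition, and #8 adds a 3-point change as clinically meaningful. It would be wrong to say that every secondary is judged on the 25% criterion, or on the p-value alone.
- **Not every null is plausible.** The plan takes UV to cause AKs and CPD, so a fully null family overstates the risk for those correlations.
- **The link to the indication is narrow.** Section 3 states the purpose as reducing AKs. It does not say that PROMIS, CPD or correlation results will support the indication, but it does not exclude them either.

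Section 10.4.2 also leaves open whether the t-test or the stepwise regression decides endpoint #1. That is a separate question, and neither the number of secondary tests nor the change proposed here settles it.

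**Conclusion.** Section 10.4.9 is wrong as written. About 16 secondary tests are planned at two-sided 0.05 with nothing to control them or to mark them as descriptive. The family-wise error is up to about 56% if all 16 are independent and null, roughly 47 to 53% under the assumed within-family correlations, and at most about 46% for the 12 between-arm tests. Even the lowest figure in the working, 33%, is more than six times 5%, so the need to act does not depend on the exact value.

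A reader might infer that a false secondary claim is more likely than not. The documents do not support that: 0.56 needs full independence and every null true, and modest changes to either assumption bring the rate to one half or below. Adding the #9 tests would raise it (ten more independent tests on a base of 0.48 give 1 − 0.52 × 0.95^10 = 0.69), but their number is not stated, and they compare characteristics of usage groups rather than test an effect of the device.

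Nor does the point reach the primary result. There is one primary endpoint, and its error rate is not changed by the number of secondary tests.

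**What to change.** Replace 10.4.9 with a statement that endpoint #1 is the only confirmatory endpoint, at two-sided 0.05. Endpoints #2 to #9 are reported as estimates with 95% confidence intervals and nominal p-values, and are not described as statistically significant or as confirming an effect. Align the success wording in 10.4.3 for #3 to #8 with this.

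If the sponsor wants a secondary to support the indication, test it only if #1 succeeds, using Holm over a fixed family of seven between-arm tests:

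- #2
- the group effect from the #3 model, with the coefficient named in advance
- #4
- one CPD measure at the last visit for #7
- the three PROMIS domains at visit 3

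The smallest p-value then has to be at or below 0.05/7 = 0.0071. The condition on #1 matters: without it, the error across #1 and the Holm family could reach 1 − 0.95^2 = 0.0975 if the two were independent.

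The cost is one paragraph plus small wording changes, with no effect on data collection or sample size. The downside is that fewer secondary results can be called significant.

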## 10.4.10 TABULATION OF INDIVIDUAL RESPONSE DATA

Clinical data tables will be reduced into a table of individual responses for analysis as follows:

Column	Source (name of CRF with data)
SubjectID	N/A
AK baseline (count)	Actinic Keratosis
AK follow up (cumulative count)	Actinic Keratosis
NMSC baseline (count)	NMSC
NMSC follow up (cumulative count)	NMSC
Observant % of days	Compliance database
Responsive Y/N	Shade database: days with UV limit below 90% of exposures
CPD R 0	Lab data
CPD R 12 month	Lab data
MHA 1	PROMIS MHA visit 1
MHA 2	PROMIS MHA visit 2
MHA 3	PROMIS MHA visit 3
MHD 1	PROMIS MHD
MHD 2	PROMIS MHD
MHD 3	PROMIS MHD
SHP 1	PROMIS SHP
SHP 2	PROMIS SHP
SHP 3	PROMIS SHP
UV Ave	Sensor data
AE (count)	CRF
comment	

group	Randomization
exclude	

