#### 10.4.2 ANALYSIS OF THE PRIMARY EFFICACY ENDPOINT(S)

##### **#1 (Primary): Quantify the impact of Shade on the cumulative number of new actinic keratoses developed over the study period.**

To test our primary aim, we will perform a control versus study group analysis. The study group will receive a Shade sensor and Shade app while the control group will standard of care sun avoidance counseling. The study will be randomized and single-blinded as described in section 10.6.1. This will also allow us to control for the effect of UV level variation on the primary outcome since the two groups will have balanced enrollment dates. All the patients will receive recommendations about UV exposure protection as defined by the recommendations of the American Academy of Dermatology and the National Cancer Institute.

Patients who will have used the Shade sensor for less than 15% of the days over the study period will be excluded from these analyses. We will use a Student's t-test with the following null and alternative hypothesis:

$$H_0: \text{mean}^C_{t12} (\text{AK}) = \text{mean}^I_{t12} (\text{AK})$$

$$H_a: \text{mean}^C_{t12} (\text{AK}) \neq \text{mean}^I_{t12} (\text{AK})$$

where  $\text{mean}^C_{t12} (\text{AK})$  is the averaged cumulative number of AK between enrollment follow up of controls and  $\text{mean}^I_{t12} (\text{AK})$  is the averaged cumulative number of AK of intervention patients.

In this analysis, demographic and clinical factors such as gender, age, baseline count of AKs, skin type, immunosuppressive treatment and comorbidity can be confounding factors. To test and control for confounding, demographic and clinical data (skin type, living area, gender, age, count of AK at enrollment, immunosuppressive (IS) treatment, level of immunosuppression and comorbidity) will be collected. We will use a stepwise multivariate approach with backward selection: 1) the effect of potential confounding factors will be tested using the same statistical tests, 2) factors with p-value <0.2 and less than 25% of missing values will be included in the multivariate model and 3) only covariates with significant adjusted p-value (<0.05) will be kept in the final model. Clinically relevant interactions will also be tested (e.g. skin type, gender, age) and kept in the final model if significant. The adjusted effect of Shade use will be estimated using a multivariate linear regression.

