#### **14.4 PUBLICATION AND DATA SHARING POLICY**

Sponsor and Investigators are committed to enhancing the value of research and furthering the advancement of public knowledge as well as to the development of its commercial products and the protection of its intellectual property. We recognize that this project will result in the collection of data useful to the research community. Therefore, final research data will be shared openly and timely in accordance with the most recent NIH guidelines ([http://grants.nih.gov/grants/policy/data\\_sharing](http://grants.nih.gov/grants/policy/data_sharing)) while being mindful that the confidentiality and privacy of participants in research must be protected at all times. Timelines for distribution of data will vary depending on any required restrictions in accordance with federal and/or institutional policies and guidelines. In general, we expect the

data will be available through publications, presentations at scientific symposia and seminars. In some cases, Shade may determine that a licensing program may be necessary to better serve the public and the research community whether or not patents have been filed. Efforts will be made to publish our research findings in scientific journals. All final peer-reviewed manuscripts that arise from this proposal will be submitted to the digital archive PubMed Central.

In order to protect the identity of subjects in this study, a more detailed discussion of the clinical data collected in this project is required. Data will come from two sources which will be handled differently.

Data collected from the clinic itself will include subject demographics including race, gender, Fitzpatrick skin type, in addition to key metadata related to the study hypothesis including transplant status, prior cancer history and prior history of actinic keratosis. These data will be published in an appropriately aggregated tabular form.

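### The baseline skin-cancer (NMSC) count is tabulated, but no analysis names it as a covariate for the skin-cancer endpoints #3 and #4; this can cost precision, though it causes no bias

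*Combined protocol and SAP*

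**What the plan says.** The table of individual responses in section 10.4.10 has a column "NMSC baseline (count" followed by "NMSC follow up (cumulative count", both sourced from the NMSC case report form. Section 14.4 adds that the clinic data include "transplant status, prior cancer history and prior history of actinic keratosis", mentioned there for aggregate publication.

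Section 10.4.3 sets out the two skin-cancer analyses:

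- **#3 (SCC):** a linear mixed model whose named terms are study group and time. On adjustment it says: "A similar stepwise multivariate approach with backward selection as described in the primary aim will be performed to take into account confounding factors".
- **#4 (all NMSC):** a t-test on cumulative counts, followed by the same kind of stepwise adjustment, "as described in the primary aim will be perform to take into account confounding factors".

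The procedure they borrow is in section 10.4.2. Its candidates are "skin type, living area, gender, age, count of AK at enrollment, immunosuppressive (IS) treatment, level of immunosuppression and comorbidity". A candidate must first reach p<0.2, and then "only covariates with significant adjusted p-value (<0.05) will be kept in the final model".

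Nothing else in section 10.4 uses the baseline NMSC count. Analysis #6 correlates UV exposure with new NMSC without adjustment, and the baseline descriptives in 10.4.6 are demographic only.

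**The concern.** A baseline value of the outcome is often the most useful covariate in a randomised comparison. If new skin cancers cluster in patients who have had them before, a model without the baseline count leaves that between-patient variation in the error term. Any chance difference between the arms in skin-cancer history also goes uncorrected. The plan follows this logic for AK, whose enrolment count is a named candidate, but not for skin cancer, although the column is in the table.

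The retention rule adds to the problem. Even if the count were offered as a candidate, a p<0.05 rule lets the data decide whether it enters, and with few events a useful covariate can fail that test.

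At stake is the width of the intervals for #3 and #4. With power as low as shown below, the estimate and its interval are the useful output of these analyses.

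**Working it through.** **The plan's own figure.** The only stated power, 0.81 for a 25% effect with 50 per arm (section 10.5), is for AK. It cannot be reproduced because the clinical AK distribution is not given. With a one-sided test, as in that simulation, it implies a CV of 0.25 / [(1.645 + 0.878) × √(2/50)] = 0.25 / 0.505 = 0.495. It says nothing about NMSC, so what follows is a range under stated assumptions.

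**Inputs.**
- From the documents: 120 patients, 1:1, so 60 per arm (4.1); two-sided 0.05 (10.4.1); 25% reduction (10.4.3).
- Assumed: patient NMSC rates are gamma-distributed with mean m per follow-up period and between-patient CV c, and the baseline count carries f follow-up periods of information.

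**Step 1: raw baseline count against no covariate.** The share of follow-up variance explained is

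R² = (f m² c²)² / [(m + m² c²)(f m + f² m² c²)], and the SE ratio is √(1 − R²).

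- m = 0.4, c = 1.5, so m²c² = 0.36. With f = 1: 0.1296 / (0.76 × 0.76) = 0.22, SE ratio 0.88. With f = 4: 2.0736 / (0.76 × 7.36) = 0.37, SE ratio 0.79.
- m = 0.1, c = 1, so m²c² = 0.01. With f = 1: 0.0001 / (0.11 × 0.11) = 0.01. With f = 4: 0.0016 / (0.11 × 0.56) = 0.03. SE ratio 0.99 or higher.

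Over m from 0.1 to 0.8, c from 1 to 2 and f = 1 or 4, R² runs from 0.01 to 0.71.

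**Step 2: why step 1 overstates the gain.** First, a skewed count would be entered as log(1 + count). At m = 0.4, c = 1.5, f = 4, that lowers R² from 0.37 to about 0.31, and √(1 − 0.31) = 0.83, so the reduction in SE is 17% and not 21%. Second, baseline AK count is already a candidate, so the fair question is what the NMSC count adds to it.

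**Step 3: log(1 + count) added to baseline AK count (simulation).** These results also assume a correlation between AK and NMSC rates.

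| NMSC per patient | CV | Further reduction in SE |
|---|---|---|
| 0.4 | 1.5 | about 8-16% |
| 0.4 | 1.0 | 2-6% |
| 0.8 | 1.5 | 14-22% |
| 0.1 | 1.0 | about 1% or less |

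In the first row, other assumed AK-NMSC correlations (0.3 to 0.7) gave 6-14% and 7-14%. A reduction of 8-16% is worth 1/0.92² = 1.18 to 1/0.84² = 1.42 times the patients.

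**Step 4: power for a 25% reduction.** At m = 0.4, c = 1.5, the control variance is 0.4 + 0.16 × 2.25 = 0.76 and the treated variance is 0.3 + 0.09 × 2.25 = 0.5025. The SE of the difference is √[(0.76 + 0.5025)/60] = 0.145 for a difference of 0.1. Then z = 0.69 and two-sided power is about 0.11. Dividing z by 0.92 or 0.84 gives 0.75 or 0.82, and power of about 0.12 or 0.13. (This ignores the little that AK count itself contributes.) Simulations with and without the raw count agree: 0.10 to 0.11-0.13 here, about 0.065-0.07 either way at 0.1 per patient, and 0.12-0.18 to 0.19-0.25 at 1.0 per patient.

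**Step 5: the retention rule.** At 0.1 NMSC per patient, 60 per arm, a p<0.05 rule kept the baseline count in only 22-61% of simulated trials.

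**The case against.** A reader might infer that the estimates for #3 and #4 are certainly less precise than the data allow. The documents do not support that. The loss depends on an event rate and a correlation they do not give. Follow-up may be as short as about six months (visit 2 at three months, the final visit at least three months later), and entry requires an AK history, not a prior cancer. NMSC may therefore be rare and the gain close to nil. This stands, and it makes the claim conditional.

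A reader might also infer bias. Randomisation rules that out: the omission affects precision and chance imbalance only.

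The plan does not strictly exclude the count. The adjustment is called similar, not identical, the list contains an undefined comorbidity item, and #3 does not say whether the enrolment value enters as a time point. That is true, but none of these names the count, and a candidate admitted that way would still face the p<0.2 and p<0.05 rules.

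Three further limits stand:
- The column covers all NMSC, so it matches #4 directly but is only a proxy for the SCC endpoint #3.
- Section 10.4.10 does not say whether baseline means lesions found at visit 1 or past history. If visit 1, the column may be mostly zeros.
- Replacing the whole candidate list with this one covariate would go too far. It would drop baseline AK count and the Fitzpatrick stratum used in the randomisation (10.6.1). With rare events (0.1 per patient, CV 1, assumed correlation 0.7), AK count alone explains about 3% of variance against 1-2% for the log NMSC count.

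**Conclusion.** The point holds in conditional form. The baseline NMSC count is in the analysis table, no analysis names it, and the borrowed procedure would not reliably bring it in. Whether this costs anything material depends on quantities outside the documents: a worthwhile gain if NMSC are fairly common and cluster within patients, and next to nothing if they are rare. The step 3 figures rest on gamma-Poisson rates, an assumed AK-NMSC correlation, and a baseline count worth one to four follow-up periods. Adjustment tightens the estimate but does not rescue the test of a 25% reduction. Severity is low: the endpoints are secondary, there is no bias, and no conclusion is likely to turn on it.

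**What to change.** 1. **#4 in section 10.4.3:** add log(1 + baseline NMSC count) as a pre-specified covariate kept whatever its p-value, alongside baseline AK count and the Fitzpatrick stratum and not instead of them. Report the Shade effect with its 95% CI from that model.
2. **#3:** do the same, using a baseline SCC count if the NMSC case report form separates SCC, and otherwise the NMSC count, described as a proxy. State whether the enrolment value is also an outcome time point in the mixed model.
3. **Section 10.4.10:** before unblinding, state whether baseline means lesions found at visit 1 or prior history. If it means visit 1 lesions, name prior skin cancer (yes/no) as the covariate now, so that the choice is not made after seeing how many zeros there are. Confirm that the cancer history collected identifies skin cancer.

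The cost is wording and one degree of freedom per model. The column already exists. The downside is little gain if NMSC prove rare.
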